#### **Infection Control/PPE - Guidelines**

**Research participants will only come on-site if absolutely necessary for study procedures.**

**Research participants need to complete the online screening the day they come to the NYSPI building and must be met at one of the entrances by research/clinical staff in order to enter.**

**COVID/COVID-like symptoms of participants will be reported to the IRB via PRISM as an SAE.**

You can upload charts or diagrams if any

## **Assessment Instruments**

Create a table or give a brief description of the instruments that will be used for assessment

### **Study 1: Surveys of Correction Officers**

---

Correction Officer Surveys: will measure three constructs from Social Cognitive Theory (behavioral capabilities (knowledge/skills), expectations, self-efficacy), as well as social distance stigma, while keeping the survey to approximately 10 minutes.

### **Study 2: Clinical Interviews with Detainees Referred by Correctional Health Services as having First Episode Psychosis**

Screening Form with Mini Mental State Examination (MMSE) (attached) **Since some aspects of the MMSE include visual components or physical movements (i.e. folding a piece of paper), during phone or video assessments, only the first 5 questions of the MMSE on orientation will be read.**

Assessment Packet (attached), will be used to collect sociodemographic information, and history of previous arrests.

A slightly modified version of the Alcohol, Smoking and Substance Involvement Screening Test (ASSIST) will be used to ascertain information about participants' substance use behaviors.

Structured Clinical Interview for the Positive and Negative Syndrome Scale (SCI-PANSS) will be conducted to better understand the severity of the participants' symptoms, which is necessary fundamental knowledge to be able to assess the dates required in the SOS below.

Symptom Onset in Schizophrenia (SOS) inventory SOS criteria will be used to determine when hallucinations and/or delusions met the threshold for psychosis. The interview-based date identifies the onset of symptoms, specifically when the severity of the symptom met clinical criteria, and the symptom occurred often enough to meet or exceed the required frequency.

Year 2: Working Alliance Inventory - Short Revised (WAI-SR): The clinician version is a 10-item measure and the client version is a 12-item measure. Items measure agreement on goals, tasks, and development of an effective bond between client and therapist. Clinicians and detainees will rate working alliance by measuring the relationship or alliance between client and therapist

Year 2: Service Engagement Scale (SES): Is a 14-item measure that asks clinicians about their client's availability (being available for arranged appointment), collaboration (participating in the management of illness), help seeking (seeking help when needed), and treatment adherence (client's attitude toward taking medication).

Year 2: Singh O'Brien Level of Engagement (SOLES): Is a 13-item client-rated scale measuring engagement with mental health services in people with psychosis.

### **Study 3: Interviews with Key Stakeholders to Assess Acceptability**

Interviews and focus groups will be designed to answer the following two overarching research questions: (1) To what extent is the new intervention suitable and satisfying to users? and (2) What barriers and facilitators do users of the intervention report experiencing? Specific interview and focus group questions will be targeted to the specific stakeholder groups but will focus on content and mode of delivery,

satisfaction with the TEC and SEESS, intent to continue using it, perceived demand, perceived appropriateness, and fit within the organizational culture of the jail and CSC programs.

Please attach copies, unless standard instruments are used

## **Research Related Delay to Treatment**

Will research procedures result in a delay to treatment?

No

Treatment to be provided at the end of the study

N/A

## **Risks/Discomforts/Inconveniences**

Risks that could be encountered during the study period

### **Study 1: Surveys of Correction Officers**

We do not foresee any risks for Correction Officers. Their participation is completely voluntary and the information collected will be confidential and anonymous, and will not be disclosed outside of the research team.

### **Study 2: Clinical Interviews with Detainees Referred by Correctional Health Services as having First Episode Psychosis.**

Participants will be asked to notify the assessor of any physical or psychological discomfort during the interview. Additionally, the research assessors will be trained to identify for signs of distress. There is a risk that information about the patient may be disclosed to other people outside of the research study. Protections of confidentiality guard against this risk, thereby minimizing the risk of such disclosure. An important ethical concern that we will seriously attend to is the possibility that identified detainees could perceive coercion to participate. During the consent process, we will clearly explain that their decision to participate or not will not be reported to anyone at any correctional agencies or mental health facilities and will not impact their legal status or relationship with service providers in any way.

### **Study 3: Interviews with Key Stakeholders to Assess Acceptability**

We do not foresee any risks to participants taking part in interviews or focus groups for this qualitative study. Their participation is completely voluntary and the information collected will be confidential and will not be disclosed outside of the research team.

Describe procedures for minimizing risks

### **Study 1: Surveys of Correction Officers**

Any risk of perceived coercion will be addressed by fully informing participants that their decision to participate is voluntary and will not be reported to anyone outside of the research team. We (or in the event that we cannot distribute the surveys due to social distancing, the Deputy Wardens and Captains) will explain that their decision will in no way impact their relationship with their employer or others. Risks to confidentiality also will be minimized. Participants' names and other potential identifiers will not be included in the dataset and each participant will be assigned a unique ID number. Surveys will be made anonymous by using a unique code created by the participant, as in [name] prior survey-based research. For example, on the front page of the survey, respondents will be asked:

- What is the first letter of your middle name?
- What is the first letter of the street you live on?
- What is the last digit of the year you were born?
- What is the last two digits of your Social Security Number?

Doing so will create a unique identification code for each participant (e.g., JB223, TF189) to ensure anonymity, while allowing us to match any participants who complete a later survey (at 6 months or 12 months).

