**Sample #1: Correction Officers**

The implementation of the Target Educational Campaign (TEC) will involve Correction Officers working at three jails: the Anna M. Kross Center (AMKC), the Rose M. Singer Center (RMSC), and the Robert N. Davoren Complex (RNDC), all located on Rikers Island in New York City. Correction Officers in these three jails will be approached to complete brief surveys. The study will need 540 completed surveys over the course of the three time points (180 surveys at each). Since identifying information is not being collected from the Correction Officers, it is possible that some of Correction Officers will participate more than once, meaning less than 540 Officers total will participate.

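### The officer matching code uses facts an employer ordinarily holds and one that changes on moving, so it neither secures anonymity nor links every repeat respondent

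*Protocol*

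**What the plan says.** Under the procedures for minimizing risks (Study 1), the Protocol describes a self-generated code, introduced with "For example, on the front page of the survey, respondents will be asked". Four items follow: the initial of the officer's middle name; a street item, worded "What is the first letter of the street you live on"; the final digit of the birth year; and a Social Security item, worded "What is the last two digits of your Social Security Number".

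The two specimen codes printed there, JB223 and TF189, fit these items: two letters, one digit, two digits. The stated purpose is "to ensure anonymity, while allowing us to match any participants who complete a later survey (at 6 months or 12 months"). The same section says potential identifiers will be kept out of the dataset.

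The description of Sample #1 gives the reason that distinct officers cannot be counted exactly: "Since identifying information is not being collected from the Correction Officers". It plans 180 surveys at each of three time points, 540 in all, and allows that some officers will take part more than once. The Waiver of Documentation of Consent rests the officer survey on the absence of identifiable information.

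Under Recruitment Procedures (Study 1), the research team normally approaches officers itself. If COVID-19 rules keep the team out at 6 or 12 months, Deputy Wardens and Captains distribute the forms, and officers put completed ones in a container in the canteen or another communal space. Neither sealing nor custody of that container is described.

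**The concern.** The code has two jobs, and the listed items weaken both.

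**Anonymity.** An employer would ordinarily have middle name, home address, birth year and Social Security number on file. A code made from fragments of these is private from a stranger but not from someone with personnel records. It sits on the front page of the form, and in the contingency that form rests in the workplace. The survey covers knowledge, expectations, self-efficacy and social distance stigma, where candor toward an employer may matter. The claim of anonymity also supports the waiver of documentation.

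**Linkage.** The street initial is the one item of the four likely to change within 12 months. An officer without a middle name has no defined answer and may answer differently at different waves. A failed match counts a repeat respondent as a new officer. That shrinks the linked subset, inflates the count of distinct officers and leaves correlation between an officer's surveys unaccounted for.

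**Working it through.** The Protocol states no code size, match rate or roster size, so there is no figure of its own to reproduce beyond 3 x 180 = 540, which is correct.

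**Inputs from the Protocol:** two letters (at most 26 values each), one digit (10), two digits (100); 180 surveys per wave.

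**Assumptions:** roster N of 1,000 to 3,000 officers; letters either uniform over 26 values or concentrated as if only 10 were in use; 5% to 20% of officers move in a year; a new street has the same initial with probability 1/26 (uniform) or 1/12 (concentrated); the employer holds all four items.

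**1. Code size K**

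- Uniform letters: 26 x 26 x 10 x 100 = 676,000.
- Ten effective letters: 10 x 10 x 10 x 100 = 100,000.

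**2. Probability that a given officer's code is unique on the roster: (1 - 1/K)^(N - 1)**

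| K | N = 1,000 | N = 3,000 |
|---|---|---|
| 676,000 | 0.9985 | 0.9956 |
| 100,000 | 0.9901 | 0.9705 |

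So about 97% to 99.9% of codes point to one person, given both the form and the personnel data.

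**3. True repeat pairs lost to an exact match at 12 months: move rate x (1 - probability of the same initial)**

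- Low end: 0.05 x 11/12 = 0.046.
- High end: 0.20 x 25/26 = 0.192.

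The loss is about 5% to 19%, so roughly 81% to 95% of pairs survive. At 6 months, with 1 - (1 - annual rate)^0.5 as the share who have moved and the factor 11/12, the loss is about 2% to 10%.

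**4. Expected chance false pairs between two waves: 180 x 180 / K = 32,400 / K**

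| Matching rule | Uniform letters | Ten effective letters |
|---|---|---|
| Full code | 32,400 / 676,000 = 0.05 | 32,400 / 100,000 = 0.32 |
| Street letter ignored | 32,400 / 26,000 = 1.25 | 32,400 / 10,000 = 3.24 |

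Dropping or ignoring the street letter therefore has a price of about 1 to 3 false pairs per wave pair. Replacing it is better than deleting it.

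**The case against.** Several objections have weight.

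- **Access.** Under Risks, the Protocol limits disclosure to the research team, and in the normal mode that team approaches officers itself. Supervisors distribute forms only in a contingency confined to the two follow-up waves, and nothing says they collect or read them. A reader might infer that the surveys are identifiable to the employer as the study is run. The documents do not support that: it takes both the completed forms and a cross-match to personnel files, and no passage says the employer holds the items.
- **Most matches survive.** A reader might also infer that repeat matching will fail in general. The figures above show the opposite.
- **Limited statistical harm.** Study Procedures (Study 1) defines the target as change in mean scores and fixes no paired analysis. The number of repeaters is not given; if it were 20 of 180 (illustrative), one to four links would be lost. With positive within-officer correlation, treating repeats as independent usually overstates the standard error of a change between waves, which is conservative.
- **Candor.** Any bias is unquantified and would largely cancel from a change score if equal across waves. Equality is not assured, because the contingency changes the handling of forms only at follow-up.
- **Status of the list.** The items are offered as an example and may not be final. They are, however, the only items given, and the specimen codes follow them.
- **Matching rule.** A near-match rule may properly sit in an analysis plan that is not shown, so its absence is not part of this point. The choice of items is made in the Protocol.

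These objections narrow the point to conditional re-identification and partial loss of links. They do not rescue the claim that this code ensures anonymity.

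**Conclusion.** The point holds in limited form. The claims that the code ensures anonymity and that no identifiable information is collected are too strong for a code that is unique for about 97% to 99.9% of officers on an assumed roster of 1,000 to 3,000. The surveys are re-identifiable if the employer obtains the forms and holds the four items, most plausibly through the contingency container. Some repeat matches, about 5% to 19% by 12 months at assumed move rates of 5% to 20%, would fail an exact match. The cost is in linked pairs, precision and the count of distinct officers; estimates of wave means do not depend on the links. An effect on candor is plausible, but the documents give no basis for its direction or size.

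**What to change.** **If the code can still be changed:** replace the street and Social Security items, and ideally the other two, with stable facts the employer does not hold, such as the first letter of the mother's first name, the first letter of the first school and the number of older siblings. If the middle name item stays, print a fixed answer for officers without one. Middle initial and birth-year digit alone give 26 x 10 = 260 cells, or about 4 to 12 officers per cell on the assumed roster, so keeping them leaves some narrowing.

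Keep the code large enough. Those two retained items plus two new letters give 26 x 26 x 26 x 10 = 175,760 combinations with uniform letters (32,400 / 175,760 = 0.18 false pairs). With ten effective letters they give only 10,000 (3.24), before the sibling item reduces this. Each item removed should therefore be matched by at least one added.

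**For the contingency:** use sealed returns or collection by the research team. Otherwise describe the surveys as coded and confidential rather than anonymous, and align the wording in the waiver section and Sample #1.

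**If baseline forms already carry the current code:** the Protocol does not say, though a contingency confined to follow-up suggests they may. New items would then break every link to baseline. Keep the code, accept matches that differ only in the street letter, and run exact matching as a sensitivity analysis. The downside is about 1 to 3 expected false pairs per comparison of two waves. This repairs linkage only, so the return safeguard or the change of wording is still needed.

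The cost is two or three reworded cover-page questions, one matching rule and a means of sealed return.

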### **Study 2: Clinical Interviews with Detainees Referred by Correctional Health Services as having First Episode Psychosis.**

The potential minor risks of physical or psychological distress will be protected against using measures taken to ensure that participants are comfortable during enrollment. If enrollment causes detectable distress, breaks will be given or enrollment will be postponed/rescheduled. Before beginning a phone or video interview (during times where social distancing guidelines are in place), the assessors will ensure they have the phone number of clinical staff currently in the clinic area, in case there is a need for a clinician to check in on the participant at any time. Any risk of perceived coercion will be addressed by fully informing participants that their decision to participate is voluntary and will not be reported to anyone outside of the research team. We will explain that their decision will in no way impact their relationship with mental health service providers or others. Risks to confidentiality also will be minimized. Consent forms with participants' signatures will be securely stored in a locked file cabinet in a locked research office in a secure building at the university. Participants' names and other potential identifiers will not be included in the dataset and each participant will be assigned a unique ID number. All initial screenings and interviews will be conducted in the same interview rooms or spaces that Correctional Health Services staff use for their meetings/counseling sessions with patients. Information pertaining to individual participants will only be released with their informed and written consent, except in unusual cases where withholding such information might pose a serious risk or danger to the participant or others. Publications and presentations will not report names, initials, or descriptors that could in any way violate confidentiality. These efforts to protect against potential risks are expected to be very effective, as they have been for our prior research.

### **Study 3: Interviews with Key Stakeholders to Assess Acceptability**

Any risk of perceived coercion will be addressed by fully informing participants that their decision to participate is voluntary and will not be reported to anyone outside of the research team. We will explain that their decision will in no way impact their relationship with their employer or others.

## Methods to Protect Confidentiality

Describe methods to protect confidentiality

We will collect some identifiable information that will be used for the purpose of determining basic eligibility criteria, and we will carefully protect such information. All information collected will be confidential and will not be disclosed outside of the research team. We will keep all records private and confidential to the extent permitted by law.

All initial screenings and interviews will be conducted in the same private interview rooms/spaces used by Correctional Health Services staff for meetings and counseling sessions. Consent forms with participants' signatures will be securely stored in a locked file cabinet in a locked research office in a secure building. Subjects' name and other potential identifiers will not be included in the notes or dataset, and each participant in the study will be assigned a unique ID number. The only link between identifying information and the unique ID number will be the paper consent forms. Information pertaining to individual participants will only be released with their informed and written consent, except in unusual cases where withholding such information might pose a serious risk or danger to the participant or others. Publications and presentations will not report names, initials, or descriptors that could in any way violate confidentiality. These efforts to protect against potential risks are expected to be very effective, as they have been for our prior research.

*Will the study be conducted under a certificate of confidentiality?*

Yes, we have already received a Certificate of Confidentiality

## Direct Benefits to Subjects

Direct Benefits to Subjects

There may be no definite direct benefits to individual participants of the proposed study. Given the minimal risks and potential benefits of the proposed research to participants and the significant potential benefit of knowledge gained, there is no evidence that the risk-benefit ratio would suggest changes to the research plan at the present time.

## Compensation and/or Reimbursement

Will compensation or reimbursement for expenses be offered to subjects?

Yes

Please describe and indicate total amount and schedule of payment(s).

Include justification for compensation amounts and indicate if there are bonus payments.

**Study 1 - Surveys of Correction Officers:** there is no monetary compensation for this study, but officers will be offered a small piece of candy or a snack item as a thank you for participating.

**Study 2 - Clinical Interviews with Detainees Referred by Correctional Health Services as having First Episode Psychosis:** there is no compensation for this study

**Study 3 - Interviews with Key Stakeholders to Assess Acceptability:** Subjects who participate in interviews, who were previously engaged by the SEESS while detained, will be compensated \$50 for their time and effort. Other subjects who participate in focus groups (SEESS staff, Correction Officers and leadership, and Correctional Health Service staff) will not be compensated (on-duty employees cannot be compensated at the agencies).

## Uploads

- Upload copy(ies) of unbolded Consent Form(s)
- Upload copy(ies) of bolded Consent Form(s)
- Upload copy(ies) of unbolded Information Sheet(s)

Upload copy(ies) of bolded Information Sheet(s)

Upload a copy of Certificate of Confidentiality

Upload copy(ies) of the HIPAA form

hipaa form 4.29.22.pdf

Upload any additional documents that may be related to this study

